3.2 Eligibility Requirements

Only those who meet all of the inclusion criteria and none of the exclusion criteria will be enrolled in this study.

Inclusion criteria:

- Moderate to severe corneal ulcer that is smear positive for filamentous fungus
- Pinhole visual acuity worse than 20/70 in the affected eye
- Age 18 years or greater, and less than or equal to 70 years
- Basic understanding of the study as determined by the physician
- Commitment to return for follow up visits

Exclusion criteria:

- Gram stain positive for bacteria or evidence of other concomitant infection (i.e. herpes, acanthameoba)
- Impending or frank perforation at recruitment
- Involvement of sclera at presentation
- Non-infectious or autoimmune keratitis
- History of corneal transplantation or recent intraocular surgery
- No light perception in the affected eye
- Pinhole visual acuity worse than 20/200 in the unaffected eye
- Pregnant women
- Participants who are decisionally and/or cognitively impaired

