3.4 Study visits

3.4.1 Baseline Visit. During this visit, eligible patients at Pondicherry will be enrolled in the study and will give consent. The baseline patient form will be completed and BSCVA obtained. All study participants will begin topical therapy with hourly 5% natamycin immediately. They will have baseline photography and OCT. They will then be randomized to either intrastromal voriconazole plus natamycin or topical natamycin alone. Those randomized to intrastromal injection will undergo this procedure in the operating theatre within 24 hours. They will have an additional 2 stromal injections: one on the 3rd day and one on the 5th day. All patients will be admitted to the inpatient setting until the 7th day.

3.4.2 Procedure visit. Within 24 hours of the baseline visit study participants randomized to intrastromal voriconazole will undergo injection in the operating theatre. They will have 2 additional rounds of intrastromal voriconazole injections: one on the 3rd day and one on the 5th day of the study.

3.4.3 Day 3 visit. During this visit, study participants will have slit lamp examination and undergo repeat scraping and culture of the corneal ulcer. Adverse events will also be assessed and recorded. Thereafter, all additional treatments including but not limited to topical voriconazole, or oral ketoconazole, will be at the clinician's discretion. The treating physician will remain masked to treatment arm. After the scraping and culture have been performed, participants randomized to receive intrastromal voriconazole injections will receive an additional injection of voriconazole in the operating theatre.

3.4.5 Day 5 visit. On day 5 participants randomized to receive intrastromal voriconazole injections will receive their final injection of voriconazole in the operating theatre.

3.4.6 Week 1 visit. Approximately one week from enrollment patients will undergo repeat scraping and culture. No other study visit information will be gathered during this visit, therefore any further examination, testing, or treatment will be at the discretion of the treating physician. After the Day 7th day, patients may be discharged from the inpatient setting.

3.4.7 One Month visit. During this visit, study participants will have their BSCVA, slit lamp examination, and OCT performed during this visit. Photography will also be performed. Adverse events will be reviewed and recorded.

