3.5 Study Schedule

	Visit 1 Baseline Exam	Visit 2 Procedure	Visit 3 Day 3	Visit 4 Day 5	Visit 5 Week 1	Visit 6 Month 1	Visit 7 Month 3
Forms							
Consent and Authorization form	X						
Baseline form	X						
Procedure form		X	X	X			
IND-VFQ							X
Follow-up form			X		X	X	X
Final form							X
Procedures							
Intrastromal		X	X	X			
Smear/culture	X		X		X		
Tests							
IOP	X		X			X	X
Topography							X
OCT	X					X	X
Slit lamp photography*	X					X	X
BSCVA/ETDRS/MRx	X					X	X
Endothelial cell count							X
Total visit time	2 hours	2 hours	2 hours	2 hours	1 hour	1 hour	1 hour
* Slit lamp photography also taken upon an adverse event							

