Mycotic Antimicrobial Localized Injection

Statistical Analysis Plan

Aravind Eye Hospital, Pondicherry, India
Francis I. Proctor Foundation, University of California San Francisco, USA

Investigators:

[name], DO DNB FICO*¹

[name], DO DNB FICO*¹

[name], DO DNB FICO*¹

[name], MD²

[name]*²

*Principal Investigator

¹Aravind Eye Hospital, Pondicherry, India

² Francis I. Proctor Foundation, University of California San Francisco, San Francisco, California, USA

MALIN Statistical Analysis Plan

Table of Contents

1. Background	1
2. Sample Size and Randomization.....	1
3. Baseline Characteristics	1
4. Primary Analysis.....	1
5. Secondary Analyses	1
6. Interim Analysis.....	2

1. Background

Mycotic Antimicrobial Localized Injection (MALIN) is a randomized, double-masked, two-arm clinical trial. The purpose of this study is to determine if intrastromal injection with voriconazole in combination with topical natamycin is superior to topical natamycin alone. Study participant's eyes will be randomized to one of two treatment groups – 1.) Topical natamycin alone or 2.) Topical natamycin plus intrastromal voriconazole injections.

2. Sample Size and Randomization

If we enroll 70 study participants we estimate that we will have over 80% power to detect a 25% difference in repeat culture status (50% in the control group vs. 25% in the voriconazole group), assuming a two-tailed alpha 0.05% and no loss to follow up (since participants will be hospitalized after enrollment until the 3-day repeat cultures are taken). Participants will be randomized using random block sizes in Microsoft Excel ([name]).

3. Baseline Characteristics

Baseline characteristics between the 2 arms will be compared using Fisher exact test for categorical variables and Wilcoxon rank sum test for continuous variables.

4. Primary Analysis

The primary study analysis will be microbiological cure at 3 days. We will compare 3-day culture positivity between the two groups using a logistic regression model (dichotomous culture positive or culture negative outcome) controlling for baseline culture status. Protocol for obtaining cultures is outlined in the MOP.

5. Secondary Analyses

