- We will compare BSCVA between the two groups, at the 3-month time period (between 2.5-3.5 months) using the Wilcoxon rank sum with a 2-sided alpha of 0.05. For study participants who experience perforation or undergo TPK this will be noted and a BSCVA will be performed prior to performing further surgery, this last observation will be carried forward (LOCF) as the 3-month BSCVA. An enhanced analysis using standard longitudinal modeling methods will be used to handle data from study participants who are lost to follow up.
- We will compare 7-day culture positivity between the two groups using a logistic regression model (dichotomous culture positive or culture negative outcome) controlling for baseline culture status
- Scar size as measured on clinical exam and photographs
- Corneal topography
- Corneal Thickness and scar size as measured by OCT
- IND-VFQ will be compared between the two groups controlling for baseline VFQ
- Analyses of perforations or other adverse events
- A cost effectiveness analysis will be performed

6. Interim Monitoring

A masked interim analysis will be conducted to re-evaluate sample size based on 3-day culture positivity when one-third of the data have been collected. A medical monitor will be appointed at UCSF to monitor any serious adverse events. A small DSMC at UCSF will be appointed to conduct an un-masked interim analysis to evaluate for futility or harm.

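### Three-month BSCVA (Aim 2) is tested without adjusting for baseline BSCVA, which is measured before randomisation; prespecified adjustment would gain precision at almost no cost

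*SAP*

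**What the plan says.** BSCVA at 3 months is Specific Aim 2 (Protocol 1.1) and the first-listed secondary outcome (Protocol 1.2), although no formal hierarchy is set. SAP section 5 states: "We will compare BSCVA between the two groups, at the 3-month time period (between 2.5-3.5 months) using the Wilcoxon rank sum", at a two-sided alpha of 0.05. It names no covariate, effect estimate or confidence interval. An eye that perforates or undergoes TPK has its pre-surgery BSCVA carried forward as the 3-month value.

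One further BSCVA analysis is planned: "An enhanced analysis using standard longitudinal modeling methods will be used to handle data from study participants who are lost to follow up". Its form is not given and no baseline term is named.

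The baseline value exists. Protocol 3.4.1 states: "The baseline patient form will be completed and BSCVA obtained", and places randomisation after that. The row "BSCVA/ETDRS/MRx" in the Protocol 3.5 schedule is marked at baseline, month 1 and month 3.

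Other outcomes in the SAP are adjusted. Three-day culture (section 4) and 7-day culture (section 5) are each analysed "using a logistic regression model (dichotomous culture positive or culture negative outcome) controlling for baseline culture status". IND-VFQ is to be adjusted for its baseline value, although the schedule marks IND-VFQ at month 3 only.

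**The concern.** Presenting acuity is an obvious candidate predictor of 3-month acuity, and the eligible range is wide. Its upper end is "Pinhole visual acuity worse than 20/70 in the affected eye". The exclusion "No light perception in the affected eye" means that eyes with light perception only can enter. If baseline acuity predicts the outcome, a test that ignores it leaves explainable variation in the error term.

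The plan adjusts culture for baseline status, and even proposes to adjust IND-VFQ for a value it does not schedule. The baseline BSCVA that it does collect goes unused in the main comparison.

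At stake is the chance of answering Aim 2. Enrolment of 70 was chosen for 3-day culture (SAP section 2), and the documents state no power for BSCVA. Naming only a test also means that Aim 2 could be reported as a p-value with no measure of how large the difference is.

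**Working it through.** **The plan's own figure.** There is none for BSCVA. The only stated power concerns 3-day culture and does not bear on this point.

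**Inputs from the documents.** 70 participants (SAP 2), allocated 1:1 (Protocol 1.3), so 35 per arm; two-sided alpha 0.05 (SAP 5).

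**Assumptions.** r from 0 to 0.7; a treatment shift of 0.6 SD; all 70 eyes contribute a 3-month value. None of these is in the documents.

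**Step 1: variance.** Linear adjustment for a baseline covariate multiplies the residual variance by 1 − r². The equivalent unadjusted sample size is 70/(1 − r²). At r = 0.5 the factor is 1 − 0.25 = 0.75, and 70/0.75 = 93.

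**Step 2: power.** Trials with 35 per arm were simulated, 20,000 per cell. They compared the tie-corrected rank-sum test with rank ANCOVA (least squares on ranks, with arm and baseline rank as terms). The no-ties case is bivariate normal. The tied case puts 40% of baseline values and 25% of control 3-month values at a common poor-acuity limit.

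| r | Variance reduction | Equivalent N (linear) | Rank-sum, no ties | Rank ANCOVA, no ties | Rank-sum, tied | Rank ANCOVA, tied | Mean width of adjusted 95% CI (SD; linear, no ties) |
|---|---|---|---|---|---|---|---|
| 0 | 0% | 70 | 67.0% | 66.7% | 66.0% | 65.8% | 0.96 |
| 0.2 | 4% | 73 | 67.8% | 69.4% | 67.2% | 68.1% | 0.94 |
| 0.3 | 9% | 77 | 67.0% | 70.7% | 66.5% | 69.4% | 0.91 |
| 0.5 | 25% | 93 | 67.4% | 78.3% | 66.2% | 75.9% | 0.83 |
| 0.6 | 36% | 109 | 67.5% | 83.6% | 66.7% | 81.4% | 0.77 |
| 0.7 | 49% | 137 | 66.7% | 90.2% | 66.3% | 87.7% | 0.68 |

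With no treatment effect, both tests rejected in 4.6-5.3% of trials.

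**Step 3: detectable difference.** At 80% power the rank-sum test detects (1.960 + 0.842) × √(2/35 ÷ 0.955) = 0.685 SD, where 0.955 = 3/π is its relative efficiency under normality. Linear ANCOVA at r = 0.5 detects 2.802 × √(2/35 × 0.75) = 0.58 SD.

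**Step 4: equivalent N for the rank-based test.** The figures in the table apply to the linear model. For rank ANCOVA the ratio can be taken from the simulated powers: at r = 0.5 without ties, [(1.96 + 0.78)/(1.96 + 0.45)]² ≈ 1.29, or about 91 participants. The tied case gives about 88. At r = 0.7 the range is about 120-130.

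**Step 5: carried-forward values.** The runs above do not model the carry-forward rule. As a sensitivity case, 20% of eyes in each arm were placed at the worst rank (an assumed rate and an assumed position). If surgery is unrelated to baseline acuity, rank-sum against rank ANCOVA power is 33% vs 33% at r = 0.3, 33% vs 36% at r = 0.5 and 34% vs 40% at r = 0.7, where r applies to the remaining eyes. At r = 0.5 the gain ranges from 3 to 8 points, depending on whether baseline acuity predicts surgery. With 30% of eyes at the worst rank and no such relation, it is about 1 point. Rank ANCOVA was not materially worse in any of these cases.

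**The case against.** Nothing in the plan is in error here. The rank-sum test is valid under randomisation, needs only an ordering of non-letter acuities, and is applied to a secondary outcome for which no power is claimed. The gain depends on an r that the documents do not give, and restricting entry to poor acuity could lower it. At r = 0.2 the gain is 1-2 points and at r = 0.3 it is 3-4. Carried-forward values after perforation or TPK can shrink it further. The longitudinal model may include baseline BSCVA, and the sample-size re-evaluation in SAP section 6 means that N may not stay at 70.

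Most of this stands as a limit on size. The gain of 9-12 points or more from r = 0.5 upward holds for the scenarios without carried-forward values and should not be read as a forecast. The missing effect estimate is a related reporting gap and does not itself argue for adjustment.

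It does not remove the case for adjusting. The proposed test is also rank-based, so robustness to skewed and tied acuity is kept. At r = 0 the loss is 0.3 points or less (67.0% vs 66.7%; 66.0% vs 65.8% with ties). The longitudinal model is stated only for loss to follow-up, so an adjusted comparison is not prespecified as the text stands. A change in N would not alter the relative gain.

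**Conclusion.** The concern holds. The main analysis of Aim 2 ignores a prognostic candidate that is measured before randomisation and already collected. The consequence is lost precision, not bias or an inflated type I error.

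Under the assumptions used (0.6 SD shift, 35 per arm, no carried-forward values), adjustment adds at most about 2 points of power at r of 0.2 or less, 3-4 at r = 0.3, 10-11 at r = 0.5 and 21-24 at r = 0.7. With a substantial share of eyes at a carried-forward worst value, the gain at r = 0.5 falls to between about 1 and 8 points. Confidence in the size is moderate because r, the SD and the surgery rate are not in the documents. The direction is secure: there is little to lose at any r and a useful gain if baseline acuity predicts outcome. The change should be made, but the trial does not fail without it.

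**What to change.** Before unmasked data are seen, amend SAP section 5 as follows:

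- Make the main BSCVA analysis a rank-based ANCOVA of 3-month BSCVA on treatment arm and baseline BSCVA, at two-sided alpha 0.05.
- Report beside it the baseline-adjusted difference in logMAR with a 95% CI, from linear regression on arm and baseline.
- State the numeric coding for non-letter acuities that the logMAR estimate needs; neither document gives one.
- Keep the unadjusted Wilcoxon test as a sensitivity analysis.
- Specify the longitudinal model and name baseline BSCVA in it.

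The cost is a few sentences and one coding table. No new data, visits or participants are needed. Fixing the choice in advance also protects the result from the charge that adjustment was chosen after seeing the data.

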Studies of intrastromal injection of voriconazole have yielded mixed results. Several case series have found intrastromal voriconazole to be beneficial.¹⁰⁻¹² However, one randomized controlled trial, comparing intrastromal injection to topical voriconazole found significantly improved 3-month visual acuity in the topical voriconazole group.¹³ However, in the intrastromal voriconazole arm there were more central ulcers than in the topical voriconazole arm and scar size between the two groups was comparable implying that intrastromal injection does not lead to worse scarring. In this study we will evaluate the effectiveness of intrastromal voriconazole injection in addition to topical natamycin treatment for the treatment of moderate to severe fungal keratitis.

Research Question: Is intrastromal injection of voriconazole beneficial in addition to topical natamycin in the treatment of filamentous fungal corneal ulcers?

1.1 Specific Aims:

- 1) **Does the addition of intrastromal injection of voriconazole decrease the rate of repeat 3-day culture positivity compared with medical management?** We hypothesize that there will be decreased 3-day repeat culture positivity in the intrastromal voriconazole injection group.
- 2) **Does intrastromal injection of voriconazole improve best spectacle corrected visual acuity at 3 months compared with medical management?** We hypothesize that intrastromal injection with voriconazole will improve 3-month visual acuity compared with topical natamycin alone.
- 3) **Does the addition of intrastromal injection of voriconazole improve 3-month scar size, days to re-epithelialization and rate of perforation/need for Therapeutic penetrating keratoplasty (TPK) compared with medical management?** We hypothesize that there will be improved 3-month scar size and decreased perforation rate in the intrastromal voriconazole group, but no difference in days to re-epithelialization.

1.2 Study Outcomes:

Primary Outcome:

- Microbiological cure on 3-day repeat cultures

Secondary Outcomes:

- BSCVA at 3 months
- Microbiological cure on 7-day repeat cultures
- Scar size/depth, as measured by clinical exam, slit lamp photographs and OCT
- Adverse events including rate of perforation/need for TPK
- Thinning as measured by pachymetry and OCT
- Topography
- Difference in IND-VFQ at 3 months between groups
- Corneal neovascularization, as measured by clinical exam & slit lamp photographs

1.3 Study Design:

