3.4.8 Final Visit. At the 3- Month visit study participants will have their BSCVA and slit lamp examination recorded, in addition to repeat photography, topography and OCT and be administered the IND-VFQ. Endothelial cell count will also be measured. Adverse events will be reviewed and recorded.

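### The SAP adjusts IND-VFQ for a baseline score that the protocol never schedules, so the analysis cannot be run as written

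*SAP*

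**What the plan says.** SAP section 5 (Secondary Analyses) gives the IND-VFQ one line: "IND-VFQ will be compared between the two groups controlling for baseline VFQ". It names no test or model beyond that adjustment.

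The protocol describes the collection of this outcome in several places:

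- Section 1.2 lists the secondary outcome as "Difference in IND-VFQ at 3 months between groups". It mentions neither a baseline score nor a change score.
- Section 3.4.1 (Baseline Visit) says "The baseline patient form will be completed and BSCVA obtained" and "They will have baseline photography and OCT". It names no questionnaire.
- Section 3.4.8 (Final Visit) has BSCVA and slit lamp examination recorded, "in addition to repeat photography, topography and OCT and be administered the IND-VFQ". No other visit description mentions the instrument.
- Section 3.5 (Study Schedule) gives the IND-VFQ a row of its own under the forms. The row has a single mark, under Visit 7, Month 3, and its Visit 1 cell is empty.

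**The concern.** The SAP model conditions on a variable that the protocol does not collect. A baseline score cannot be recovered later, because topical treatment begins at the baseline visit itself and the eye's condition then changes.

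The analysis at stake is a pre-specified secondary analysis of the only questionnaire in the schedule. The SAP gives no fallback, so someone would have to choose a replacement. If the gap is noticed only at the analysis stage, that choice would be made with outcome data in hand, which is what pre-specification is meant to prevent.

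**Working it through.** The plan states no power, sample size or precision figure for the IND-VFQ, so there is no figure to reproduce. The check has two parts.

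**1. Is a baseline score scheduled anywhere?**

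| Visit | Protocol visit text (3.4) | IND-VFQ mark in 3.5 |
|---|---|---|
| 1 Baseline | Form, BSCVA, photography, OCT | None |
| 2 Procedure | Injection | None |
| 3 Day 3 | Slit lamp, scraping and culture, adverse events | None |
| 4 Day 5 | Injection | None |
| 5 Week 1 | Scraping and culture; "No other study visit information will be gathered during this visit" | None |
| 6 Month 1 | BSCVA, slit lamp, OCT, photography, adverse events | None |
| 7 Month 3 | IND-VFQ named | X |

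The mark in the IND-VFQ row falls in the seventh of seven visit columns. The consent and baseline form rows beside it do carry a Visit 1 mark, so the blank cell is not a column lost when the table was read.

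Scheduled administrations: 1 at Month 3 and 0 at baseline. The SAP plans 70 participants, so the covariate is missing for 70 of 70.

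**2. What would the lost adjustment be worth?**

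Let r be the within-arm correlation between baseline and Month 3 scores. Neither document gives r, so 0.3 to 0.6 is an assumption. Adjusting for baseline multiplies the residual variance by about 1 − r². The unadjusted sample size that matches 70 adjusted participants is 70 / (1 − r²), and the unadjusted standard error is larger by a factor of 1 / √(1 − r²).

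- r = 0.3: 1 − 0.09 = 0.91; 70 / 0.91 = 77; standard error ratio 1 / √0.91 = 1.05.
- r = 0.6: 1 − 0.36 = 0.64; 70 / 0.64 = 109; standard error ratio 1 / √0.64 = 1.25.

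Over this range, losing the covariate gives up 9% to 36% of the variance and widens the confidence interval by about 5% to 25%. Using 70 also assumes that everyone reaches Month 3. With fewer completers both sample sizes shrink in proportion, but the ratios do not change.

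**The case against.** The strongest counter-argument is that the score may be collected after all. Neither the baseline form nor the manual of procedures cited in the SAP is among the documents. The silence of Protocol 3.4.1 is weak evidence, because that text also omits IOP and the smear and culture, both of which the schedule marks at Visit 1. That is fair, and a questionnaire inside the baseline form cannot be strictly excluded. But the schedule treats the IND-VFQ as a form separate from the baseline, follow-up and final forms. At Month 3 it is marked in addition to the follow-up and final forms. A baseline administration would be expected to have its own mark. If one is intended, the schedule is wrong and still needs correcting.

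A second argument is that little is lost. The Month 3 difference is valid without adjustment, Protocol 1.2 already words the outcome that way, and the IND-VFQ is one of eight secondary outcomes, so the primary conclusion is untouched. This stands as a limit on severity. It does not remove the conflict: section 1.2 names an outcome but no test or model, and the SAP line still prescribes an adjustment that cannot be made. The SAP can be amended before unmasking, so a data-driven choice is avoidable, but only if the gap is dealt with now.

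A third argument is that the 77 to 109 range is illustrative. It is. No stated precision target for the IND-VFQ is missed, since the 70 was set on 3-day culture status.

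**Conclusion.** The concern holds. As the protocol schedules data collection, the IND-VFQ analysis in SAP section 5 cannot be run, because its covariate would not exist for any participant. That conclusion rests only on the two documents and does not depend on r.

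The cost in precision is less certain: equivalent to 77 to 109 unadjusted participants in place of 70 if r is 0.3 to 0.6, with r assumed. The one reservation is the unseen baseline form. This point should be corrected, but it does not threaten the primary analysis.

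**What to change.** Make the two documents agree in one of two ways.

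1. **Collect the baseline score.** Mark the IND-VFQ at Visit 1 in Protocol 3.5 and add it to 3.4.1, to be completed before randomisation. The SAP line can then stay, with its regression model named. The cost is one questionnaire within a visit already scheduled at 2 hours, plus a schedule edit. This works only for participants not yet enrolled.
2. **Change the SAP line.** The minimal edit deletes the baseline VFQ adjustment and names a test for the Month 3 score, which matches Protocol 1.2. Alternatively, specify a linear regression of the Month 3 IND-VFQ score on treatment arm and baseline BSCVA, which is already obtained at Visit 1. The cost is one line of SAP wording. How much precision BSCVA would recover is unknown. Neither document relates it to the IND-VFQ, and eligibility requires pinhole acuity worse than 20/70 in the affected eye, which narrows its range.

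If enrolment is complete, only the second route remains. In either case, date the change before unmasked outcome data are seen. If the baseline form does already contain the questionnaire, correct the schedule and section 3.4.1 to say so.
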